Disease	Incidence	Expected cases	Single marker study	MWAS	GWAS
Death (all cause)	612	12240	1.08	1.16	1.14
Type 2 diabetes	950	19000	1.06	1.13	1.11
Cardiovascular disease Cancer (all cause)	864 625	17280 12500	1.06 1.06 1.08	1.13	1.11
Myocardial infarction	453	9060	1.09	1.19	1.16
Stroke	221	4420	1.14	1.19	1.24
Breast cancer (F)	251	2510	1.19	1.39	1.32
Prostate cancer (M)	158	1580	1.23	1.51	1.42
Colo-rectal cancer	47	940	1.31	1.69	1.56
Pancreatic cancer	22	440	1.47	2.12	1.89
Stomach cancer	18	360	1.52	2.28	2.01
End stage renal failure	15	300	1.59	2.45	2.14

References

1. Collaboration NCDRF. Worldwide trends in diabetes since 1980: a pooled analysis of 751 population-based studies with 4.4 million participants. Lancet. 2016;387(10027):1513-30.

2. collaborators NCDC. NCD Countdown 2030: worldwide trends in non-communicable disease mortality and progress towards Sustainable Development Goal target 3.4. Lancet. 2018;392(10152):1072-88.

3. Collaboration NCDRF. Worldwide trends in diabetes since 1980: a pooled analysis of 751 population-based studies with 4.4 million participants. Lancet. 2016;387(10027):1513-30.

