Diabetes and cardiovascular disease are 2-4 fold more common in UK South Asians than Europeans. The reasons underlying this health disparity are not known. To advance understanding of metabolic, cardiovascular and other important chronic diseases in UK South Asians, we propose to establish LOLIPOP 100K, a longitudinal population study comprising ~100,000 South Asian and European men and women, aged 25-85 years, under long-term follow-up for health outcomes. We will deliver this by building on our previously completed initial LOLIPOP study, comprising 30,000 people and carried out in 2002-8. In this new phase we extend this previous work and recruit up to 100,000 new South Asian men and women to create LOLIPOP 100K. Recruitment will be via GP lists and coordinated centrally to allow targeting of South Asians and Europeans, and enable monitoring of participation by factors including age, sex, socioeconomic status. All participants will be asked for their consent to participate and will have baseline assessment moving through a series of 'assessment stations' including guestionnaires, physical measurements and blood/urine sampling. Baseline assessment will be of ~ 90 mins duration. Assessment will be carried out by staff (nurses / health care assistants) trained specifically for the LOLIPOP 100K Study. Data will be collected using a customised, integrated IT system. Blood samples will be processed in the central laboratory, and aliquots will be stored at -80°C for future analysis.

Participants will be followed-up for their health long-term through medical and other health-related records. We aim to use a range of data sources including linkage for: i. death; ii. site-specific cancer, iii. Hospital Episode Statistics (HES) for England and Wales; Scottish Morbidity Record (SMR) for Scotland; iv. myocardial infarction (MINAP), stroke (SINAP); v. pathology services at local hospitals; vi. hospital databases (CVD, T2D, ESRD, histopathology); vii. primary-care electronic health records. The data and samples will be used to investigate the behavioural, environmental, genetic and other molecular factors influencing health and disease in South Asian populations.

2. Background

Importance of cardiovascular disease and diabetes in South Asian populations

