Potential participants will identified from GP practice lists and invited to attend an appointment at dedicated LOLIPOP 100K research clinics. SMS text invitations will be sent out to potential participants by the respective GP (in partnership with the Primary Care Research Network) and depending on response rate letters of invitation will also be sent to potential participants by the respective GP (in partnership with the Primary Care Research Network). The invitation letter will include options of date and time of appointment. Potential participants will be asked to confirm their appointment by; i. telephoning the central booking office; ii. email; iii. mailing the reply form in the pre-paid envelope provided or; iv. on-line visiting the study website. Potential participants who agree to attend for assessment will be sent a written confirmation of their appointment, along with advice on preparations for attending the assessment centre, and to record information that they might have difficulty recalling during the visit (e.g. medications, operations). We anticipate a response rate of ~50%, based on previous experience in the completed LOLIPOP study, and thus to invite ~ 200,000 people to take part, to achieve our goal of recruiting 100,000 people to the LOLIOP 100K study.

The central booking office will be available to confirm, change, cancel appointments and allow questions from potential participants to be addressed (e.g. transport and parking; travel expenses; assessment centre procedures; consent and withdrawal; feedback of results; confidentiality). Potential participants who confirm an assessment visit appointment but then do not attend will be sent a letter within 1-2 weeks of the missed appointment. This will ask them to contact the freephone service to book another appointment if they might still like to participate.

Knowledge about the research will also be promoted through community activities including open meetings with the public, meetings with community organisations and our study website. Members of the community who are interested to participate in the research, and who meet study entry criteria, will have the opportunity to register for the study.

Study visit

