Assessment centres will be in hospital or community locations with good public transport links, proximity to parking, and disabled access. Usual opening hours will be typically Monday to Friday 8.00 am to 8.00 pm and Weekends 8.00 am to 5.00 pm. Assessment centres will be staffed by nurses, healthcare assistants, technicians and receptionist and senior nurse manager. All staff will be fully trained in baseline assessments. Participants will be asked to attend for a health evaluation after an overnight fast (water only after midnight). All participants will complete a structured assessment by the research team, comprising: i. Registration and consent; ii. Questionnaire; iii. Physical measurements; iv. Biological samples and v. Physical activity monitoring. The baseline assessment expected to take approximately two hours.

i. Registration and consent

Written, informed consent will be obtained from all participants for data collection, and inclusion in the research. Given the approach to recruitment, all participants will have had at least 24 hours to consider whether to take part. Informed consent will include permission for the data and samples collected to be used for chronic disease research, including data sharing with national and international bodies concerned with prevention and control of T2D and CVD, as well as for molecular epidemiological research. Participants will be given the opportunity to ask questions during the consent discussion. Multilingual research facilitators fluent in the major South Asian languages (Punjabi, Hindi, Urdu) will be available as necessary to facilitate collection of informed consent. Participants unable to give informed consent will not be recruited.

ii. Questionnaires will comprise:

- a. Health and lifestyle questionnaire will be used to collect information on behavioural risk factors (smoking, alcohol habit, physical activity), personal and family medical history, medications, socio-economic status and other measures of lifestyle and environmental exposure.
- b. Dietary habit by interviewer administered 24-hour dietary recall, using the online digital platform "INTAKE24" (https://intake24.co.uk/). This does not store identifiable data.

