The assessments proposed are all non-invasive, well established and safe. They have all been successfully used in large scale population studies such as UK Biobank, involving >500,000 Europeans, and have been shown to be feasible and acceptable to participants. The research team have considerable experience in the assessments proposed through their other completed and ongoing population research studies.

8. Sample management

Biological samples (blood, urine and stool) will be collected from participants. Aliquots of whole blood, serum, plasma and urine will be stored for future quantification of biomarkers for cardiovascular and metabolic health (eg measurement of lipid profile, renal function and insulin levels), and as a resource for future molecular epidemiological studies to investigate the mechanisms underpinning the development of CVD, T2D, and other complex disease that are of importance to South Asian populations (including but not limited to: obesity, cancer, dementia, COPD, chronic kidney disease). The molecular epidemiological research will employ a range of strategies including, but not limited to: genome sequencing and genotyping, studies of genomic regulation (eg quantification of DNA methylation), molecular profiling of serum and urine (eg by targeted and untargeted metabolomics, or proteomics).

The aliquots of blood, urine and stool will be stored long term (>20 years) at -80C or below. All storage locations will be physically secure (eg 24 hour security staff and CC-TV), with continuous monitoring of and recording of freezer temperatures, air-conditioning and remote alarms in the event of freezer failure. To help ensure the security of this unique resource, sample aliquots from each participant will be split and stored in separate locations.

9. Incidental Clinical Findings

LOLIPOP 100K participants will be offered a report comprising physical measurements (adiposity, blood pressure), biochemistry (lipid profile, glucose, HbA1c) and clinically reported 12 lead ECG. The rationale for our approach is that these tests that are recommended by the NHS as part of routine, periodic health-check in the adult population, and are an important part of our commitment to stakeholder involvement. Our experience from the LOLIPOP study is that these health reports were well received by the participant and their GP, and were considered a valued benefit from taking part in research.

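### One fasting instruction covers all appointment times, so the fast on arrival could run from 8 hours to about 18 hours, and the protocol does not name time of last intake or of blood draw as data

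*Protocol*

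**What the plan says.** The preparation instruction is in section 6 (Study visit): "Participants will be asked to attend for a health evaluation after an overnight fast (water only after midnight"). It is not varied by appointment time. The same paragraph gives the clinic hours: "Usual opening hours will be typically Monday to Friday 8.00 am to 8.00 pm and Weekends 8.00 am to 5.00 pm". Under Recruitment in section 6, the protocol adds: "The invitation letter will include options of date and time of appointment". No section restricts fasted visits to the morning, sets a shortest or longest fast, or gives a separate instruction for later appointments.

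Several planned measures are sensitive to fasting state. The participant report in section 9 includes "biochemistry (lipid profile, glucose, HbA1c"). Section 8 plans assays on stored aliquots ("eg measurement of lipid profile, renal function and insulin levels") and also metabolomic profiling. The power table includes a metabolome-wide design.

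Blood is listed late in the visit: "iii. Physical measurements; iv. Biological samples and v. Physical activity monitoring". Section 6 lists the baseline questionnaires, measurements and samples without naming time of last food or drink, or time of venepuncture. Section 5 does not exclude people with diabetes, and section 7 (Participant risk and burden) does not mention fasting.

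**The concern.** A fasting instruction is meant to put participants in a comparable metabolic state before blood is drawn. This one fixes when the fast starts but not when it ends, and the clinic day is up to 12 hours long. A compliant participant seen at opening and one seen in the last weekday slot would have fasted for very different lengths of time, and would also be sampled at different times of day. Overnight is no longer an apt description of the second fast.

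The primary aim centres on factors that influence diabetes and cardiovascular disease, so glucose, lipids and insulin matter to it directly. Uncontrolled variation in fasting length adds noise to these measures. If appointment time happens to be related to an exposure or outcome under study, it could also add bias. Samples are to be kept for more than 20 years, and a participant's time of last intake cannot be reliably recovered later.

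There is also a participant-risk side. The population has a high burden of type 2 diabetes, ages run to 85, and the risk section does not consider what the instruction means for someone with a late appointment.

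**Working it through.** The protocol states no figure for fasting length, so there is none to reproduce. The check is clock arithmetic on its own times.

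**Inputs**
- Start of fast: midnight at the latest (section 6, Study visit).
- Opening: 08:00–20:00 on weekdays, 08:00–17:00 at weekends (same paragraph).
- Visit length: 2 h by section 6 ("The baseline assessment expected to take approximately two hours") or 1.5 h by section 1 ("Baseline assessment will be of ~ 90 mins duration"). The two differ, so both are used.

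**Formulas**
- Shortest fast on arrival = opening time − 00:00.
- Longest fast on arrival = (closing time − visit length) − 00:00.
- Longest fast by the end of the visit = closing time − 00:00.

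**Results**

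| | Shortest on arrival | Longest on arrival, 2 h visit | Longest on arrival, 1.5 h visit | By closing |
|---|---|---|---|---|
| Weekday | 8 h | 20 − 2 = 18 h | 20 − 1.5 = 18.5 h | 20 h |
| Weekend | 8 h | 17 − 2 = 15 h | 17 − 1.5 = 15.5 h | 17 h |

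The blood draw falls somewhere between arrival and the end of the visit. The outer limits at the draw are therefore 8 to 20 h on weekdays and 8 to 17 h at weekends.

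**Earlier last meal.** Midnight is only the latest permitted intake. Assume instead a last meal at 20:00 the evening before, which adds 4 h. The fast on arrival becomes 12 h to 22–22.5 h on weekdays and 12 h to 19–19.5 h at weekends.

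**Share of visits more than 12 h fasted.** The protocol does not give the distribution of appointments. Assume, for illustration, that weekday arrivals are spread evenly from opening to the last feasible slot. The share arriving after noon is then:
- 2 h visit: (18 − 12) / (18 − 8) = 6 / 10 = 60%.
- 1.5 h visit: (18.5 − 12) / (18.5 − 8) = 6.5 / 10.5 = 62%.

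The effect of these differences on glucose, lipids or insulin cannot be derived from the documents.

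**The case against.** The strongest reply is that opening hours are not fasted-appointment hours. The hours are described as usual and typical, an overnight fast fits morning attendance naturally, and the written confirmation comes with guidance on how to prepare. That guidance, a booking rule or the study SOP could deal with late slots. The list in section 6 covers assessments and devices rather than database fields, and electronic capture might time-stamp some steps. The choice of covariates can properly wait for an analysis plan.

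Part of this stands. Such safeguards may exist, and leaving covariates out of a protocol is not in itself a fault. But the protocol's own text pairs one instruction with a full clinic day and a choice of times, and says nothing to limit the result. No later analysis can adjust for a time of last intake that was not collected.

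A reader might infer more than the text supports:
- **That everyone attends fasted, or that those who eat will be recorded as fasted.** Participants are only asked to fast. The protocol gives no compliance figure and describes no fasted flag.
- **That visits begin 20 h into a fast, or that two thirds begin after noon.** Both ignore visit length. Twenty hours is reached only at closing, and even slots give 60–62%.
- **That the error differs by employment, age or ethnicity.** This is possible, but nothing in the protocol links appointment time to any of them.
- **That the analysis section treats these biomarkers as comparable regardless of fasting.** Section 12 does not say so. Its continuous examples are blood pressure, HbA1c, cholesterol and creatinine, and analysis of covariance admits covariates.
- **That every blood result in the participant report is affected.** HbA1c does not depend on fasting length.

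**Conclusion.** The point holds as a conflict within section 6. The instruction, as written, does not standardise fasting state. Longest fasts on arrival are more than double the shortest on weekdays (18–18.5 h against 8 h) and nearly double at weekends (15–15.5 h against 8 h).

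These figures assume that appointments are available throughout opening hours, that participants comply, and that the last intake is at midnight; an earlier last meal lengthens every fast. The consequence for the biomarkers is avoidable variation and possible bias of unknown size. The documents do not establish that bias exists or that it differs between ethnic groups.

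On participant risk, the finding is limited to an omission: the risk section does not discuss a fast that the protocol's own times allow to be long, in a study that does not exclude people with diabetes. A reader might go further and call the visit unsafe, but the documents give no basis for judging the degree of risk. The point should be settled before recruitment proceeds, because the missing times cannot be reliably recovered afterwards.

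**What to change.** 1. Reconcile the fasting instruction with the appointment hours in section 6. How to do this is for the investigators to decide, and no fasting or booking rule is proposed here. Have section 7 address the fast that results.
2. At every visit, record the time of last food or drink other than water and the time of venepuncture, and name both among the baseline data.
3. Use fasting duration and clock time of sampling as covariates in analyses of fasting-sensitive biomarkers (glucose, lipids, insulin, metabolomics). The detail can sit in the analysis plan.
4. In passing, align the two stated visit lengths. This moves the latest arrival by only half an hour.

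The cost is two time fields in the electronic capture system already planned and two extra covariates. Depending on how the investigators settle the first item, there may also be some change to booking.

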To address our research aims, we propose to create the LOLIPOP 100K study, an observational, longitudinal population study comprising up to 100,000 South Asian and European men and women, aged 25-85. Participants will be undergo comprehensive phenotyping, including collection of questionnaire, physical measurements, retinal imaging, and biospecimen collection. Participants will continue to be followed for at least 20 years after the last subject has been recruited to identify future health outcomes. The LOLIPOP 100K resource created will provide a powerful epidemiological tool for investigation of the risk factors and mechanisms underlying health and disease in UK South Asians.

Recruitment

Our approaches to participant recruitment will be based on our successful experience in recruiting ~30,000 participants to the completed LOLIPOP study. Recruitment will be carried out in partnership with GPs in West London and other UK regions with high South Asian populations.

Potential participants will be South Asian (originating from India, Pakistan, Sri Lanka, Bangladesh) and European men and women aged 25-85 years. There will be oversampling of South Asians to achieve an expected sample size of up to 80,000 in this ethnic group. We anticipate recruiting up to 20,000 European participants. When recruiting through postal mechanisms we anticipate that there will be some participants of other ethnic groups who are enthusiastic to take part; these individuals can provide useful information on risk factor profiles in Non-Asian ethnic groups and so will be permitted to take part.

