Local investigators should report any SAEs as required by their Local Research Ethics Committee, Sponsor and/or Research & Development Office.

Contact details for reporting SAEs

[contact]

CI email (and contact details below)

[contact], attention [name] [name]

Please send SAE forms to: [name] [name]

[contact] (Mon to Fri 09.00 – 17.00)

11. Follow-up and future recontact

Our prospective population study design proposes that participants be followed up to identify people who will maintain health or develop disease. We will then relate this to the extensive range of risk factors captured at baseline. This presents an invaluable opportunity to investigate the causes and natural history of a wide range of diseases and health conditions that affect South Asians. There are two broad approaches to follow-up that will be adopted:

 Routine record linkage. Participant consent will be sought to enable long-term follow-up for their health long term through medical and other health-related records. This will include linkage for; i. death; ii. site-specific cancer, iii. Hospital Episode Statistics (HES) for England and Wales; Scottish Morbidity Record (SMR) for Scotland; iv. myocardial infarction (MINAP), stroke (SINAP); v. pathology services at local hospitals; vi. hospital databases (CVD, T2D, ESRD, histopathology); vii. primary-care electronic health records. Since it is not possible to describe the electronic health records that will be available in the future, it is not possible to provide an exhaustive list of data sources that we will use. In general we will aim to access a wide range of systems (current and future) that hold health data as is usual practice in large scale population studies internationally.

• *Re-contact with participants.* Direct re-contact with participants provides a valuable means to capture reliable information on a wide range of risk factors and medical conditions. We will obtain consent from all participants for permission to re-contact them in future for a re-screening examination or for further evaluation based on clinical and laboratory characteristics (ie phenotype and/or genotype). This might involve attending a repeat baseline visit to the research health clinic. Follow-up using web based questionnaires may provide a cost-effective option for future contacts. Further IRB approval will be obtained before participants are recontacted for research purposes.

12. Statistical considerations

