The database design will include appropriate physical and user level data security as well as full audit trails of access. Personal and clinical data will be separated by pseudonymization to enhance data security; the code linking personal and clinical data will only be available to the study PIs. The study database manager will be responsible for dayday management of the database, including generating quality control reports and daily query logs for resolution.

Data will be stored long-term (>20 years) for research purposes. Data access will be regulated by the study investigators who will assess written requests for access to data, to ensure that the user is an appropriate health researcher or policy maker. Data access processes will be transparent and auditable, and without unreasonable barriers to appropriate use of data. We anticipate sharing data with a range of academic, clinical, governmental and commercial organisations. The study PIs will also establish outreach to potential data users to maximise the exploitation of the data for research and policy decisions. Data sharing will follow all relevant national and international guidelines and legislation; in particular, the research data will only be shared in an anonymized format (ie all personal identifiers removed) to ensure preservation of privacy of participants.

The Chief Investigator will preserve the confidentiality of participants taking part in the study and is registered under the Data Protection Act.

Imperial College

15. Withdrawal process for participants

Participants may withdraw from the study at any time. Participants will be asked to submit their request to withdraw in writing to the LOLIPOP 100K study co-ordinator (contact details TBC). Reasons for withdrawal will be documented where provided. On withdrawal, the participants identifiable samples will be destroyed and linked data withdrawn firm release for further research. If samples or data have been previously used, or are anonymised, we will not be able to retrieve them.

16. Process for payments to participants

Reasonable travel expenses incurred by the participant in attending the research clinic will be reimbursed, supported by receipts where appropriate. Researchers will not receive payment over and above normal salary for recruiting the subjects in the study.

17. List of recruiting and referring sites

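### Section 15 allows only one level of withdrawal and does not say that data and events recorded before it stay in later analyses; graded options would cheaply prevent avoidable loss

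*Protocol*

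**What the plan says.** Section numbers are those in the body of the protocol; the list of contents numbers some sections differently.

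- **Timing (Section 15).** "Participants may withdraw from the study at any time". This includes the period after a diagnosis.
- **Consequence (Section 15).** "On withdrawal, the participants identifiable samples will be destroyed and linked data withdrawn firm release for further research". No lesser level appears, and nothing is said about keeping information up to the withdrawal date.
- **Exemption (Section 15).** "If samples or data have been previously used, or are anonymised, we will not be able to retrieve them".
- **Record of withdrawal (Section 15).** Requests are made in writing. "Reasons for withdrawal will be documented where provided".
- **Form of the data (Section 14).** Outside users receive anonymised data only: "the research data will only be shared in an anonymized format". Internally the data are pseudonymised, and "the code linking personal and clinical data will only be available to the study PIs".
- **Follow-up (Section 11).** Two approaches are described: linkage to routine records, which asks nothing more of the participant, and direct re-contact. For the second, "We will obtain consent from all participants for permission to re-contact them in future for a re-screening examination or for further evaluation".
- **Duration (Section 6).** "Participants will continue to be followed for at least 20 years after the last subject has been recruited to identify future health outcomes".

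**The concern.** A cohort followed for two decades will have some participants who want no more letters or clinic visits but do not mind their records being used. Linkage could go on without involving them. Section 15 does not provide for this, nor for someone who wants linkage to stop but is content for what has been collected to be kept.

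The second gap concerns time. Withdrawal can come after the outcome. If a participant's information is then unavailable to later research, that person is not censored on the withdrawal date but is absent from the start of follow-up, in both numerator and denominator. Whether someone is in the analysis can then depend on whether disease developed. Section 12 targets prevalence, incidence and exposure associations, with odds ratios as small as 1.1 for common diseases, so modest selection could matter. Destroyed samples cannot be restored by any analysis plan.

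**Working it through.** **1. What later analyses lose.** Internal data remain linkable through the code, so the rule can be applied to them. Anonymised releases and completed analyses fall under the exemption and keep the participant. Data sets drawn before and after a withdrawal will therefore contain different people. What is withheld depends on the undefined term:

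- all data held for the participant: baseline data, person-time and events go;
- data from health-record linkage only: linked follow-up and events go;
- data tied to the destroyed samples only: laboratory data go.

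The first is the plain reading and is used below.

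**2. Inputs.** The protocol gives no withdrawal rate and no figure for the resulting bias, so there is nothing of its own to reproduce. From the power Table, cardiovascular disease incidence is 864 per 100,000 per year. By simple multiplication, 10-year risk *p* = 864 × 10 / 100,000 = 0.0864. All withdrawal rates below are assumptions.

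**3. Incidence.** With withdrawal *wc* in cases and *wn* in non-cases:

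observed risk = p(1 − wc) / [p(1 − wc) + (1 − p)(1 − wn)]

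For 5% and 1%: 0.0864 × 0.95 = 0.08208; 0.9136 × 0.99 = 0.90446; 0.08208 / 0.98654 = 0.0832; ratio to 0.0864 = 0.963.

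| Cases | Non-cases | Observed / true risk |
|---|---|---|
| 5% | 5% | 1.000 |
| 1% | 0.5% | 0.995 |
| 2% | 1% | 0.991 |
| 5% | 1% | 0.963 |
| 10% | 2% | 0.925 |

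The Table's expected count for this disease, 17,280 in 100,000, is twice 864 × 10. Using *p* = 0.1728 instead, the 5%/1% row gives 0.16416 / (0.16416 + 0.81893) = 0.1670, a ratio of 0.966. The choice of *p* hardly matters here.

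**4. Odds ratio.** With withdrawal *c1*, *c0* in exposed and unexposed cases and *n1*, *n0* in exposed and unexposed non-cases:

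observed OR = true OR × [(1 − c1)(1 − n0)] / [(1 − c0)(1 − n1)]

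Take a true OR of 1.10 and *n1* = *n0* = 1%:

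- c1 = c0 = 5% (case status alone): 1.10, unchanged
- 2% and 1%: 1.10 × 0.98/0.99 = 1.089
- 5% and 2%: 1.10 × 0.95/0.98 = 1.066
- 10% and 5%: 1.10 × 0.90/0.95 = 1.042

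**5. Precision.** For a two-sided 5% test with 90% power, two controls per case and 20% exposure, losing 5% of the Table's 300 end stage renal failure cases moves the detectable OR from 1.701 to 1.723. For type 2 diabetes (19,000 cases) it moves from 1.074 to 1.076. These baselines differ somewhat from the Table's 1.59 and 1.06, so only the shift is used. It is minor.

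**6. With the change.** If information up to withdrawal is kept and follow-up censored there, events before withdrawal stay in, and the bias from removing them is zero by construction. This holds for anyone who does not choose full withdrawal.

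**The case against.** A reader might infer three stronger things, and the text supports none of them.

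- **That withdrawal removes everything the study ever held.** The exemption for used or anonymised material says otherwise. For data, the protocol speaks of withholding from further research, not erasure; only samples are destroyed.
- **That asking for no more contact triggers full withdrawal.** Section 15 addresses people leaving the study. It does not say that a contact preference counts as that, and Section 11 makes re-contact a separate permission needing further ethical approval. The consent and withdrawal forms are not in the documents at hand and may already offer levels.
- **That the results will be biased.** Equal withdrawal in cases and non-cases biases neither measure, and dependence on case status alone leaves the odds ratio intact. The documents contain no evidence of joint dependence on outcome and exposure. It is conceivable, since Section 11 allows re-contact chosen by phenotype or genotype and Section 9 offers participants a health report, but that is a possible route and no more. A participant who has died cannot withdraw, so deaths are not removed by a later request.

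It can also be said that censoring belongs in an analysis plan, and that honouring full withdrawal is a matter of participants' rights. Both are fair. Even so, an analysis plan cannot use material that the protocol bars from use, and graded options leave full withdrawal in place. What remains is that Section 15, as the operative rule, states one level, leaves its key term undefined and does not address information from before withdrawal.

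**Conclusion.** The point holds as a cheap improvement to a stated rule. Section 15 provides one level of withdrawal, does not match the separation of linkage and re-contact in Section 11, and leaves open whether earlier data and events stay in later analyses.

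The size is conditional. On the plain reading of *linked data*, 10-year cardiovascular incidence is understated by about 4% if 5% of cases and 1% of non-cases withdraw, and by about 0.5% at 1% and 0.5%. A true OR of 1.10 falls to 1.066 only if exposed cases withdraw more than unexposed ones (5% against 2%, with non-cases equal). None of these rates comes from the protocol. Loss of power is not the issue. It would go too far to conclude that the cohort's estimates are invalid or that records are irretrievably deleted.

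**What to change.** Amend Section 15, in line with the consent and withdrawal forms, so that the participant is asked which level is meant:

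- (a) no further contact, with linkage and use of data and samples continuing;
- (b) no further contact or linkage, with data and samples to date kept and follow-up censored at the withdrawal date;
- (c) no further use, as now, with the existing exemption.

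Define *linked data*, and record the level and date of each withdrawal so that withdrawals can be counted and described. If the forms already offer levels, Section 15 need only be brought into line with them.

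The cost is a protocol and form amendment, a database entry for level and date, and staff time to explain three options. Outcome-related loss remains possible among those who choose (c), but is confined to them. An early change is better, since samples destroyed in the meantime cannot be replaced.
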